11.1.6 Assessment of Adverse Events

All AEs and SAEs whether volunteered by the patient, discovered by study personnel during questioning, or detected through physical examination, laboratory test, or other means will be reported appropriately. Each reported AE or SAE will be described by its duration (i.e., start and end dates), regulatory seriousness criteria if applicable, suspected relationship to the study drug (see following guidance), and actions taken.

To ensure consistency of AE and SAE causality assessments, investigators should apply the following general guideline:

YES: There is a plausible temporal relationship between the onset of the AE and administration of the study medication, and the AE cannot be readily explained by the patient's clinical state, intercurrent illness, or concomitant therapies, and/or the AE follows a known pattern of response to the study drug, and/or the AE abates or resolves upon discontinuation of the study drug or dose reduction and, if applicable, reappears upon re-challenge.

NO: Evidence exists that the AE has an etiology other than the study drug (e.g., preexisting medical condition, underlying disease, intercurrent illness, or concomitant medication), and/or the AE has no plausible temporal relationship to study drug administration (e.g., cancer diagnosed 2 days after first dose of study drug).

CONFIDENTIAL

STUDY DRUG(S): CARFILZOMIB AMENDMENT 2 DATE: 25 FEBRUARY 2015

11.2 Serious Adverse Event Reporting by Investigators

Adverse events classified by the treating investigator as serious require expeditious handling and reporting to SCRI Innovations SD in order to comply with regulatory requirements. Determination of life-threatening or serious is based on the opinion of either the Sponsor or the Investigator.

Serious AEs may occur at any time from the start of study treatment through the 30 days after the last dose of study drug. The SCRI Innovations SD must be notified of all SAEs, regardless of causality, within 24 hours of the first knowledge of the event by the treating physician or research personnel.

To report a SAE, the SAE Report Form should be completed with the necessary information.

The SAE report should be sent to SCRI Innovations SD via fax or e-mail using the using the following contact information (during both business and non-business hours):

SCRI Innovations Safety Department

Safety Dept. [contact]

Safety Dept. Email: [contact]

Transmission of the SAE report should be confirmed by the site personnel submitting the report.

Follow-up information for SAEs and information on non-serious AEs that become serious should also be reported to SCRI Innovations SD as soon as it is available; these reports should be submitted using the SCRI Innovations SAE Report Form. The detailed SAE reporting process will be provided to the sites in the SAE reporting guidelines contained in the study reference manual.

Investigators must report SAEs and follow-up information to their responsible IRB according to the policies of the responsible IRB.

Expedited Reporting by Investigator to Onyx

Expedited reporting will be completed by the Sponsor Safety Department of SCRI Innovations Safety Department. Expedited reports will not be sent to Onyx by the Site investigator. SAE reports are submitted by the participating site investigator with 24 hours of awareness to the SCRI Innovations Safety Department. The Expedited Reporting responsibilities belong to SCRI Innovations Safety Department.

CAR-XXX and the institutional protocol number should be included on all reports to Onyx.

Onyx Drug Safety and Pharmacovigilance Contact Information:

Onyx [contact] Email: [contact]

CONFIDENTIAL

STUDY DRUG(S): CARFILZOMIB AMENDMENT 2 DATE: 25 FEBRUARY 2015

11.3 Recording of Adverse Events and Serious Adverse Events

11.3.1 Diagnosis vs. Signs and Symptoms

All AEs should be recorded individually in the patient's own words (verbatim) unless, in the opinion of the Principal Investigator or designated physician, the AEs constitute components of a recognized condition, disease, or syndrome. In the latter case, the condition, disease, or syndrome should be named rather than each individual sign or symptom. If a constellation of signs and/or symptoms cannot be medically characterized as a single diagnosis or syndrome at the time of reporting, each individual event should be recorded as an AE or SAE as appropriate on the relevant form(s) (SAE Report Form and/or AE eCRF screen). If a diagnosis is subsequently established, it should be reported as follow-up information is available. If a diagnosis is determined subsequent to the reporting of the constellation of symptoms, the signs/symptoms should be updated to reflect the diagnosis.

Progression of malignancy (including fatal outcomes), if documented by use of appropriate method (for example, as per RECIST criteria for solid tumors), should not be reported as an SAE.

11.3.2 Persistent or Recurrent Adverse Events

A persistent AE is one that extends continuously, without resolution, between patient evaluation time points. Such events should only be recorded once on the SAE Report Form and/or the AE eCRF screen. If a persistent AE becomes more severe or lessens in severity, it should be recorded on a separate SAE Report Form and/or AE eCRF screen.

A recurrent AE is one that occurs and resolves between patient evaluation time points, and subsequently recurs. All recurrent AEs should be recorded on an SAE Report Form and/or AE eCRF screen.

11.3.3 Abnormal Laboratory Values

If an abnormal laboratory value or vital sign is associated with clinical signs and/or symptoms, the sign or symptom should be reported as an AE or SAE, and the associated laboratory value or vital sign should be considered additional information that must be collected on the relevant eCRF screen. If the laboratory abnormality is a sign of a disease or syndrome, only the diagnosis needs to be recorded on the SAE Report Form or AE eCRF screen.

Abnormal laboratory values will be reported as an AE if: the laboratory result requires an adjustment in the study drug(s) or discontinuation of treatment, and/ or laboratory findings require additional testing or surgical intervention, a laboratory result or finding is associated with accompanying symptoms, or a laboratory result is considered to be an AE by the investigator.

11.3.4 Deaths

Deaths that occur during the protocol-specified AE reporting period that are attributed by the Investigator solely to progression of disease will be recorded on the "Study Discontinuation" eCRF screen. All other on study deaths, regardless of attribution, will be recorded on an SAE Report Form and expeditiously reported to the SCRI Innovations SD.

CONFIDENTIAL

STUDY DRUG(S): CARFILZOMIB AMENDMENT 2 DATE: 25 FEBRUARY 2015

When recording a SAE with an outcome of death, the event or condition that caused or contributed to the fatal outcome should be recorded as the single medical concept on the SAE Report Form and Adverse Event screen of the eCRF. If the cause of death is unknown and cannot be ascertained at the time of reporting, record "Death NOS" on the eCRF Adverse Event screen. During post-study survival follow-up, deaths attributed to progression of disease will be recorded only on the "After Progressive Disease Follow-Up" eCRF screen.

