7.4 Response Assessment Every 3 Cycles

Patients will be evaluated for response to treatment after every 3 cycles of treatment. The following assessments will be performed:

- CT scans of chest, abdomen and pelvis (if abnormal at baseline)
- 24 hour urine for 5-HIAA

Patients with progressive disease or unacceptable toxicity should be discontinued from the study; patients with stable disease or response to therapy will continue treatment.

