11.1.2 Serious Adverse Event

An AE or a suspected adverse reaction (SAR) is considered "serious" if it results in any of the following outcomes:

- Death
- A life-threatening AE, defined as any adverse experience that places the subject, in the view of the Investigator, at immediate risk of death at the time of occurrence; i.e., it does not include a reaction that, had it occurred in a more severe form, might have caused death.
- Inpatient hospitalization of at least 24-hours or prolongation of existing hospitalization
- A persistent or significant incapacity or substantial disruption of the ability to conduct normal life functions
- A congenital anomaly/birth defect

Important medical events that may not result in death, be life-threatening, or require hospitalization may be considered serious when, based upon appropriate medical judgment, they may jeopardize the patient or subject and may require medical or surgical intervention to prevent one of the outcomes listed in this definition. Examples of such medical events include allergic bronchospasm requiring intensive treatment in an emergency room or at home, blood dyscrasias *CONFIDENTIAL*

STUDY DRUG(S): CARFILZOMIB AMENDMENT 2 DATE: 25 FEBRUARY 2015

or convulsions that do not result in hospitalization, or development of drug dependency or drug abuse.

It is important to distinguish between "serious" and "severe" AE, as the terms are not synonymous. Severity is a measure of intensity; however, an AE of severe intensity need not necessarily be considered serious. Seriousness serves as the guide for defining regulatory reporting obligations. "Serious" is a regulatory definition and is based on patient/event outcome or action usually associated with events that pose a threat to a patient's life or vital functions. For example, nausea which persists for several hours may be considered severe nausea, but may not be considered an SAE. On the other hand, a stroke which results in only a limited degree of disability may be considered only a mild stroke, but would be considered an SAE. Severity and seriousness should be independently assessed when recording AEs on the eCRF and SAEs on the SAE Report Form.

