11.1.5 Recording and Reporting of Adverse Events

Recording of Adverse Events

All AEs of any patient during the course of the research study will be recorded in the eCRF, and the investigator will give his or her opinion as to the relationship of the AE to the study drug treatment (i.e., whether the event is related or unrelated to study drug administration).

All AEs should be documented. A description of the event, including its date of onset and resolution, whether it constitutes a serious adverse event (SAE) or not, any action taken (e.g., changes to study treatment), and outcome, should be provided, along with the investigator's assessment of causality (i.e., the relationship to the study treatment[s]). For an AE to be a suspected treatment-related event there should be at least a reasonable possibility of a causal relationship between the protocol treatment and the AE. Adverse events will be graded according to the NCI CTCAE v4.03, and changes will be documented.

If the AE is serious, it should be reported immediately to SCRI Innovations SD. Other untoward events occurring in the framework of a clinical study are to be recorded as AEs (i.e., AEs that occur prior to assignment of study treatment that are related to a protocol-mandated intervention, including invasive procedures such as biopsies, medication washout, or no treatment run-in).

CONFIDENTIAL

STUDY DRUG(S): CARFILZOMIB AMENDMENT 2 DATE: 25 FEBRUARY 2015

Any clinically significant signs and symptoms; abnormal test findings; changes in physical examination; hypersensitivity; and other measurements that occur will be reported as an AE, and collected on the relevant eCRF screen.

Test findings will be reported as an AE if: the test result requires an adjustment in the study drug(s) or discontinuation of treatment, and/ or test findings require additional testing or surgical intervention, a test result or finding is associated with accompanying symptoms, or a test result is considered to be an AE by the investigator.

Reporting Period for Adverse Events

All AEs regardless of seriousness or relationship to carfilzomib treatment (called study treatment), spanning from the start of study treatment, until 30 calendar days after discontinuation or completion of study treatment as defined by the clinical study for that patient, are to be recorded on the corresponding screen(s) included in the eCRF.

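### Sections 11.3.1 and 11.3.4 disagree on whether progression must be documented before a death attributed to it is exempt from SAE reporting

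*Combined protocol and SAP*

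**What the plan says.** Two sections of the protocol deal with death from disease.

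- Section 11.3.4 (Deaths): "Deaths that occur during the protocol-specified AE reporting period that are attributed by the Investigator solely to progression of disease will be recorded". The place named for this is the study-discontinuation screen of the eCRF, and the investigator's attribution is the only condition. For the remaining deaths the section says: "All other on study deaths, regardless of attribution, will be recorded on an SAE Report Form and expeditiously reported to the SCRI Innovations SD".
- Section 11.3.1 (Diagnosis vs. Signs and Symptoms): "Progression of malignancy (including fatal outcomes), if documented by use of appropriate method", with RECIST given as an example, is not to be reported as an SAE. Here documentation is the condition.

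Three general rules surround them. Section 11.1.2 lists death first among the outcomes that make an event serious. Section 11.2 says: "The SCRI Innovations SD must be notified of all SAEs, regardless of causality, within 24 hours of the first knowledge of the event". Section 11.1.5 sets the reporting period, "spanning from the start of study treatment, until 30 calendar days after discontinuation or completion of study treatment".

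On imaging, Section 7.4 says: "Patients will be evaluated for response to treatment after every 3 cycles of treatment". Section 5 sets the cycle at 28 days. On analysis, the safety part of Section 10.4.1 plans summaries of SAEs, of AEs leading to discontinuation, of AEs by maximum grade and of related AEs. It names no summary or listing of deaths.

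**The concern.** One death can meet the exemption in 11.3.4 and fail the condition in 11.3.1. A site that follows 11.3.4 then completes a discontinuation screen, while a site that follows 11.3.1 with 11.2 sends an SAE report within 24 hours. Handling would depend on which section the site happened to read.

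What is at stake is a second opinion on cause. Section 11.2 lets either the sponsor or the investigator judge seriousness, and Section 11.4.1 lets either suspect a relation to the drug. If the investigator's attribution alone keeps the death off the SAE form, the safety department does not receive it by the route on which its own judgement depends. The trial has a single arm, so a misattributed death cannot show up as an imbalance between groups. Section 6.2 anticipates heart failure, renal dysfunction and tumour lysis on treatment, so the cause of an early death may not be obvious.

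**Working it through.** The plan gives no figure on this point to reproduce. The check sets the rules side by side, then looks at timing and size.

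**1. The rules applied to each kind of death in the AE reporting period**

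| Death | 11.3.1 read with 11.1.2 and 11.2 | 11.3.4 | Agree? |
|---|---|---|---|
| Attributed solely to progression; progression documented | Exempt | Discontinuation screen | Yes |
| Attributed solely to progression; progression not documented | SAE within 24 hours (by inference) | Discontinuation screen | **No** |
| Attributed wholly or partly to another cause | SAE | SAE form | Yes |
| Cause unknown | SAE | SAE form; entered as Death NOS on the AE screen | Yes |

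The conflict is confined to the second row. The entry there is an inference. Section 11.3.1 states when progression is exempt and does not say what to do otherwise; the duty to report comes from 11.1.2 and 11.2 once the exemption does not apply.

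**2. When the second row is most likely**

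First scheduled response scan: 3 cycles x 28 days = 84 days. The life expectancy required at entry (Section 3.1, criterion 9) is more than 12 weeks, and 12 x 7 = 84 days. For about the first 84 days, then, no scheduled post-baseline response scan exists to document progression. This is not a period in which documentation is impossible: Section 7.5 provides for CT at the end of treatment, which may come earlier; an unscheduled scan may be done; Appendix E admits clinical measurement of superficial lesions; and 11.3.1 names RECIST only as an example.

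**3. What such a death would and would not reach**

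- Reaches: the discontinuation screen (11.3.4), PFS as a death on study (10.4.1), and the count of withdrawals (10.4).
- Remains reportable: any separate preceding AE, whatever its relation to the drug (11.1.5), and as an SAE if it meets a criterion in 11.1.2.
- Can miss: the SAE form, the 24-hour route to the safety department (11.2) and the SAE summary (10.4.1).

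**4. Size, as an illustration only**

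The documents give no expected number of early deaths. Assume one death and compare the fatal-SAE rate with and without it, using exact (Clopper-Pearson) 95% intervals: lower limit = the 0.025 quantile of Beta(x, n - x + 1), upper limit = the 0.975 quantile of Beta(x + 1, n - x). For x = 0 the lower limit is 0 and the upper limit is 1 - 0.025^(1/n).

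| n | Death counted | Death omitted |
|---|---|---|
| 62 (full accrual) | 1/62 = 1.6% (0.0 to 8.7) | 0/62 = 0% (0 to 5.8) |
| 23 (first stage) | 1/23 = 4.3% (0.1 to 21.9) | 0/23 = 0% (0 to 14.8) |

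The denominator in use would be the Safety Population of Section 10.3, which may be smaller than 62.

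**The case against.** The best defence is that 11.3.4 is the section specific to deaths and so governs them, while 11.3.1 concerns how to record diagnoses and symptoms and never says that undocumented progression must be reported. Section 11.3.7 points the same way: it keeps metastasis and its symptoms out of AE and SAE reporting with no documentation condition. That reading is reasonable, but the protocol does not adopt it. Section 11.3.1 expressly covers fatal outcomes and no section is given precedence, so the text stays open to two readings.

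The defence is right about reach. Three stronger readings are tempting, and the documents do not support them:

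- That every death without documented progression escapes. Section 11.3.4 diverts only deaths attributed solely to progression; all others, including those of unknown cause, already go on an SAE form.
- That a toxic early death vanishes from the safety data. A heart-failure, renal or tumour-lysis event before death is an AE in its own right and is not removed by 11.3.4. What can be missing is the death itself, chiefly where no separate event was recognised beforehand.
- That progression cannot be documented before day 84. It can, by the means listed in the working.

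**Conclusion.** The concern holds in a narrow form. For one class of death, attributed solely to progression in the AE reporting period but without documented progression, the two sections lead to different reporting. Such a death can miss expedited safety review and the SAE summaries. This rests on reading the condition in 11.3.1 together with 11.1.2 and 11.2, not on an explicit instruction in 11.3.1.

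The number of patients affected cannot be estimated from the documents. It may be none, and the 1.6% shows only what one omitted death would mean at full accrual. The response rate and the two-stage decision rule do not depend on how a death is reported, so the primary analysis is untouched. The point is still worth correcting: it is cheap, and it does most good if settled before any death is classified.

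**What to change.** Reconcile the two sections by carrying the documentation condition of 11.3.1, in its existing terms, into 11.3.4. A death attributed to progression would then be exempt only where progression has been documented by an appropriate method; without that, it goes on an SAE Report Form like all other on-study deaths. A reader might want to require imaging before death. Section 11.3.1 asks for neither imaging nor that timing, and the repair does not need it.

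Add to the safety analysis in Section 10.4.1 a listing of all deaths within 30 days of last dose, giving the attributed cause and the date and result of the last tumour assessment. This shows the reader every such death whichever route it took.

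The cost is amendment wording, a few additional SAE forms and one listing. Some of those forms will describe deaths that were indeed due to disease.

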11.3.5 Hospitalization, Prolonged Hospitalization, or Surgery

Any AE that results in hospitalization of >24 hours or prolongation of pre-existing hospitalization should be documented and reported as an SAE unless specifically instructed otherwise in this protocol. There are some hospitalizations that do not require reporting as an SAE.

Treatment within or admission to the following facilities is not considered to meet the criteria of "inpatient hospitalization" (although if any other SAE criteria are met, the event must still be treated as an SAE and immediately reported):

- Emergency Department or Emergency Room
- Outpatient or same-day surgery units
- Observation or short-stay unit
- Rehabilitation facility
- Hospice or skilled nursing facility
- Nursing homes, Custodial care or Respite care facility

Hospitalization during the study for a pre-planned surgical or medical procedure (one which was planned prior to entry in the study), does not require reporting as an SAE to the SCRI Innovations SD.

11.3.6 Pre-Existing Medical Conditions

A pre-existing medical condition is one that is present at the start of the study. Such conditions should be recorded on the General Medical History eCRF screen. A pre-existing medical condition should be recorded as an AE or SAE only if the frequency, severity, or character of the condition worsens during the study. When recording such events on an SAE Report Form and/or AE eCRF screen, it is important to convey the concept that the pre-existing condition has changed by including applicable descriptors.

11.3.7 New Cancers

The development of a new primary cancer should be regarded as an AE and will generally meet at least one of the seriousness criteria (see Section 11.1.2). New primary cancers are those that are not the primary reason for the administration of the study treatment and have developed after the inclusion of the patient into the study. They do not include metastases of the original cancer. Symptoms of metastasis or the metastasis itself should not be reported as an AE/SAE, as they are considered to be disease progression.

CONFIDENTIAL

STUDY DRUG(S): CARFILZOMIB AMENDMENT 2 DATE: 25 FEBRUARY 2015

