1.3.2 Clinical Experience

In the single-arm, multicenter trial of 266 multiple myeloma patients, carfilzomib produced an overall response rate (ORR) of 22.9% (95% confidence interval [CI]:18, 28.5) with a median duration of response of 7.8 months (95% CI: 5.6, 9.2). In this and other studies, carfilzomib was well tolerated and did not seem to cause clinically meaningful peripheral neuropathy. The most commonly reported adverse events (AEs) were fatigue, anemia, nausea, thrombocytopenia, dyspnea, diarrhea, and pyrexia. Subsequent studies confirming the benefit of carfilzomib in the treatment of multiple myeloma are ongoing.

In a clinical study, the pharmacokinetics and safety of carfilzomib were evaluated in patients with normal renal function vs. those with mild, moderate, and severe renal impairment, as well as in patients on chronic dialysis, treated with carfilzomib doses of 15 mg/m² during cycle 1, 20 mg/m² during cycle 2, and 27 mg/m² for cycles 3 and beyond (Badros et al. 2013).

Pharmacokinetics data available for the 15 and 20 mg/m² dose indicated that the C_{max} and AUC of carfilzomib were similar across all renal function categories following carfilzomib doses of 15 and 20 mg/m². Moreover, the overall safety profile was similar in patients in all renal function categories during mean treatment duration of 5.5 months. However, a recent report indicated 6 patients with baseline renal impairment had further renal function deterioration during the study period.

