11.1 Definitions

11.1.1 Adverse Events

Adverse event means any untoward medical occurrence associated with the use of a drug in humans, whether or not considered drug related. An adverse event (also known as adverse experience) can be any unfavorable and unintended sign (e.g., an abnormal laboratory finding), symptom, or disease temporarily associated with the use of a drug, without any judgement about causality. An adverse event can arise with any use of the drug (e.g., off-label use, use in combination with another drug) and with any route of administration, formulation, dose or including overdose.

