Progressive Disease (PD):	Appearance of one or more new lesions and/or unequivocal progression of existing non-target lesions. When the subject also has measurable disease, to achieve "unequivocal progression" on the basis of the non-target disease, there must be an overall level of substantial worsening in non-target disease such that, even in presence of SD or PR in the target disease, the overall tumor burden has increased sufficiently to merit discontinuation of therapy.		

Evaluation of Best Overall Response

The best overall response is the best response recorded from the start of the treatment until disease progression/recurrence (taking as reference for PD the smallest measurements recorded since the treatment started). In general, the subject's best response assignment will depend on the achievement of both measurement and confirmation criteria.

Confirmation of response (by repeat scans after 4 weeks or as specified in the protocol) is required for studies in which response rate is the primary endpoint, but is not required in randomized studies or studies with primary survival endpoints (i.e., where response is not a primary endpoint).

CONFIDENTIAL

Target Lesions	Non-Target Lesions	New Lesions	Overall Response	
CR	CR	NO	CR	
CR	SD	NO	PR	
CR	NE	NO	PR	
PR	SD OR NE	NO	PR	
SD	SD OR NE	NO	SD	
PD	ANY	YES OR NO	PD	
ANY	PD	YES OR NO	PD	
ANY	ANY	YES	PD	

In some circumstances, it may be difficult to distinguish residual disease from normal tissue. When the evaluation of a CR depends upon this determination, it is recommended that the residual lesion be investigated by fine needle aspirate or biopsy to confirm the CR status.

When nodal disease is included in the sum of target lesions, and the nodes decrease to "normal" size (<<10 mm), they may still have a measurement reported on scans. This measurement should be recorded even though the nodes are normal in order not to overstate progression, should it be based on increase in size of the nodes. As noted earlier, this means that subjects with CR may not have a total sum of "zero" on the eCRF.

CONFIDENTIAL

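### Section 11.3.7 keeps symptoms attributed to metastasis out of the AE and SAE records without requiring documented progression, in conflict with 11.1.1, 11.1.2, 11.1.5, 11.3.1, 11.3.6 and Appendix E

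*Combined protocol and SAP*

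**What the plan says.** Section 11.3.7 (New Cancers) first explains that a new primary cancer is an AE and that metastases of the original cancer are not new primaries. It then adds: "Symptoms of metastasis or the metastasis itself should not be reported as an AE/SAE, as they are considered to be disease progression".

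Other current sections bear on the same event:

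- Section 11.1.1 defines an AE so as to include any sign, "symptom, or disease temporarily associated with the use of a drug, without any judgement about causality".
- Section 11.1.5 requires the eCRF to hold "All AEs regardless of seriousness or relationship to carfilzomib treatment", from the start of treatment until 30 days after it ends.
- Section 11.1.2 makes an AE serious if it leads to an inpatient stay of 24 hours or more.
- Section 11.3.1 says that progression of malignancy, fatal outcomes included, "if documented by use of appropriate method (for example, as per RECIST criteria for solid tumors), should not be reported as an SAE".
- Section 11.3.6 says that a condition present at study start "should be recorded as an AE or SAE only if the frequency, severity, or character of the condition worsens during the study".
- Appendix E defines progression in target lesions by measured growth or new lesions, and in non-target disease as "Appearance of one or more new lesions and/or unequivocal progression of existing non-target lesions".

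Inclusion criterion 1 (Section 3.1) admits unresectable or metastatic disease, and criterion 6 sets separate transaminase limits for patients with liver metastases. Under Section 7.4, imaging for response follows every 3 cycles. Section 10.4.1 (Safety Analysis) bases the safety assessment on the reported incidence of treatment-emergent AEs.

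**The concern.** Evaluating toxicity is a secondary objective (Section 2.2), and there is no control arm against which disease symptoms could be netted out. In that setting the usual practice is to record every event and let attribution be a field on the record. Section 11.3.7 reverses the order: the investigator first decides whether a symptom comes from a metastasis and, if so, reports nothing as an AE or SAE.

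The background section shows why attribution is hard here. From earlier carfilzomib studies it reports: "The most commonly reported adverse events (AEs) were fatigue, anemia, nausea, thrombocytopenia, dyspnea, diarrhea, and pyrexia". Fatigue, nausea, dyspnea and diarrhea are non-specific, and an investigator could put any of them down to metastatic disease. At stake are the all-cause AE and SAE tables and the sponsor's ability to check whether an event was correctly called disease-related.

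**Working it through.** No figure in the plan depends on this rule, so there is nothing to reproduce numerically. The check sets the sections side by side.

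1. **Scope of the exemption.** Section 11.3.1 has a condition (documented by an appropriate method) and a limit (SAE only). Section 11.3.7 has neither: it covers AE and SAE and applies to symptoms with no documentation. A site holding both cannot tell which governs.

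2. **Whether the symptom is progression.** Appendix E counts measured growth, new lesions and unequivocal non-target progression. Symptoms are not a criterion. A symptom of an unchanged metastasis is therefore called progression in 11.3.7 and is not progression under Appendix E.

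3. **Order of attribution and recording.** Section 11.1.1 defines an AE with no causality judgement. Section 11.1.5 requires recording whatever the relationship, and 11.1.6 treats the suspected relationship as one descriptor of an event already reported. Section 11.3.7 needs the judgement before anything is reported.

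4. **Pre-existing conditions.** Metastases present at entry are a pre-existing condition in the ordinary sense. Under 11.3.6 a worsening in frequency, severity or character is recorded. Under 11.3.7 it is not, if it is put down to the metastasis.

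5. **Seriousness.** Take a living patient with metastases at entry who is admitted for a day or longer with diarrhea or dyspnea that the investigator attributes to them. By 11.1.2 this is serious; by 11.1.5 it is recorded; by 11.3.7 it is not reported; by Appendix E it is not progression.

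6. **Timing.** Scans every 3 cycles of 28 days are 3 × 28 = 84 days (12 weeks) apart. Even where a new metastasis is later found, its symptoms may appear well before any scan documents it, and 11.3.7 exempts them throughout.

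7. **What else would catch the event.** Section 11.3.4 gives deaths attributed solely to progression their own eCRF screen. No screen is named for a non-fatal symptom attributed to metastasis. The SUSAR process in 11.4.1 lets the sponsor, as well as the investigator, suspect a relationship, but this needs a reported event to look at.

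8. **Direction.** If the true incidence of an event is p and a share f of cases is withheld under 11.3.7, the recorded incidence is p(1 − f), which cannot exceed p. The documents give neither p nor f for this population, so the direction follows but the size does not.

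**The case against.** The best defence is context. The sentence stands under a heading on new cancers, directly after the statement that metastases are not new primaries. Read there, it may mean only that a newly arising metastasis and its symptoms are not a new-cancer event, and a new metastatic lesion is progression under Appendix E. This reading is possible, but the sentence does not state that limit. Even if it did, symptoms would be exempt before any scan had documented the lesion.

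Several other points for the plan stand:

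- Drug toxicity is not exempted as such. An event is lost as toxicity only if it is wrongly attributed, and 11.1.6 counts an event that fits the drug's known pattern as support for relatedness.
- A reader might infer a conflict with the hospitalization rule in 11.3.5. There is none: that rule gives way where the protocol specifically instructs otherwise, and 11.3.7 is such an instruction. The conflict is with 11.1.2.
- A reader might infer that a misattributed event leaves no trace. That goes too far. Sections 11.1.5 and 11.3.3 still make an AE of test findings that, for example, change or stop study drug. Laboratory results and vital signs are summarised separately under 10.4.1, concomitant medications are reviewed at treatment visits, and source records can be verified. What is missing is the AE or SAE entry.
- Recording the event would not by itself repair the table of treatment-related AEs, since the same investigator would mark it unrelated. The gain is in the all-cause tables and in giving the sponsor something to review.

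**Conclusion.** The point holds as an inconsistency in the safety-reporting rules with a one-way effect. A non-fatal symptom that an investigator attributes to metastasis, rightly or wrongly, can be left out of the AE and SAE records. All-cause AE and SAE incidence under 10.4.1 can then only be under-counted, and the sponsor cannot review the attribution. This rests on sites following the sentence as worded and on some patients having metastases at entry, which the inclusion criteria allow.

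The size is unknown. A reader might want to assume an AE rate and a share lost and quote the effect on a confidence interval. The documents supply neither input, and they plan exact intervals for ORR and CBR, not for AE rates, so such a figure would describe the assumptions and not this trial.

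A reader might also infer that symptoms called progression would enter the efficacy endpoints. The documents do not support this: 10.4.1 defines response and PFS by RECIST v1.1. The primary endpoint and the two-stage decision are untouched. The matter should be corrected, but it does not undermine the design.

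**What to change.** Reword the last sentence of 11.3.7 so that it carries the documentation condition of 11.3.1. For example:

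> A metastasis documented as progression under Appendix E is recorded as disease progression and is not itself an AE or SAE. Non-fatal new or worsened signs or symptoms attributed to metastasis are recorded as AEs (and as SAEs if they meet 11.1.2) under 11.1.5, 11.3.1 and 11.3.3, with the investigator's attribution entered as the relationship. Deaths attributed solely to progression follow 11.3.4.

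The limit to non-fatal events keeps the text consistent with 11.3.4 and with the fatal-outcome exemption in 11.3.1. The reference to 11.3.3 keeps the existing thresholds for laboratory findings. Sections 11.3.1 and 11.3.3 prefer a diagnosis to its component signs, so site guidance should add that the metastasis itself is not the diagnosis that replaces the symptom. Otherwise the event would drop out again by that route.

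The change replaces one sentence by amendment and alters no dose, endpoint or sample size. Its cost is more AE entries, some extra SAE reports, and all-cause AE rates that look slightly higher.
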